6.2.3 Product Storage and Stability

Ascor is light sensitive. Light exposure will be minimized, and vials will be stored at 2°C to 8°C prior to use. Infusion solutions will be prepared by Investigational Pharmacy (IP) during weekdays and will be placed in the ward refrigerator which is maintained at 2°C to 8°C. IP prepared infusion solutions containing vitamin C or placebo will expire in 24 hours. Infusion solutions prepared by ICU Pharmacy (9th floor Critical Care Hospital) after-hours will expire in 12 hours. There is published data establishing the stability of admixtures of ascorbic acid to be 96 hours stored at room temperature or refrigerated. [name] has unpublished data that was obtained prior to an earlier IND trial (**IND #113856**) which demonstrates the stability of samples prepared in the same manner as described below.

6.2.4 Preparation

As noted above VCU Health IP will mix L-ascorbic acid once every 24 hours in four 50 ml hooded infusion bags using aseptic technique according to USP 797 requirements. All Ascor vials utilized will be discarded within 4 hours or sooner as per the Ascor package insert. Prepared solutions are stored on the inpatient unit or ICU refrigerator in the dark at 2°C to 8°C. At designated infusion time, Nursing will infuse the contents of the light-shielded agent via infusion pump through tubing over 30 minutes. Prior studies performed have shown that L-ascorbic acid prepared for infusion in this way remains stable with no quantifiable oxidation or loss of activity.

For ascorbic acid, the volume of ascorbic acid to be added to the IV bag will be calculated. . **Under no circumstance an individual infusion dose will exceed 3.75 grams of vitamin C, or the daily infused dose above 15 grams.** This same amount of fluid will be withdrawn out of the D5%W 50 mL bag and discarded. Then, the calculated volume of ascorbic acid will be added to the infusion bag. Residual air will be removed from the infusion bag to prevent oxidation, and the bag will be shrouded. **We commit that all solutions will have a pharmacy-approved appropriate osmolarity for peripheral infusions, and the volume of placebo will be exactly the same as the control.**

Microbiologic Controls:

Investigational Pharmacy has an ISO Class 5 laminar airflow hood (Nuaire Class II Type A2 biological safety cabinet) in a segregated compounding area. This biological safety cabinet is recertified every 6 months. Compounding personnel must successfully complete media fill testing and gloved, finger-tip sampling as per USP 797 regulations.

6.3 Measures to Minimize Bias: Randomization and Blinding

The investigational pharmacist will use a standardized scientific randomization module within REDCap (36) Only the study pharmacist will have access to the online secure repository. The REDCap module has an auditing trail and log records on who accesses it as well as strict security controls.

The prepared infusion bags will have **sealed** amber shrouding to cover the IV bag in order to maintain the blind.

The randomization method will be a block (per site) and stratified and WHO COVID-19 ordinal outcomes status) randomization.

We plan to perform block randomization for each participating site. Within this block, there will be further stratification of randomization for severity of illness based on WHO COVID-19 ordinal outcome cutoff as seen in the table below:

	WHO COVID-19 scale 3-5 at enrollment	WHO COVID-19 scale 6-7 at enrollment
	Stratum A	Stratum B

The goal is for each site to have an equivalent severity among patients randomized to the treatment or placebo arm within each stratum.

6.4 Study Intervention Compliance

Adherence to the protocol will be assessed and verified using participant drug log, review of electronic medical records, and review of the eCRF.

6.5 Concomitant Therapy

Any concomitant medications as part of the standard of care (particularly antibiotics, oxygen therapy, glucose infusion, insulin, albumin, corticosteroids, N-acetylcysteine, norepinephrine, vasopressin) provided will be recorded.

6.5.1 Rescue Medicine

Not applicable.

6.5.2 List of concurrent medications that may be incompatible with intravenous vitamin C

A review of the literature discloses that no known medications are incompatible with intravenous vitamin C concurrent administration. Herein we outline three categories of interacting medications. Medication that are absolutely contraindicated (**none identified**). Medications that may interact in a harmful way, therefore we may need to consider therapy modification. For the study purposes, patients who are taking, or plan to take these medications during the period of the study will be excluded. Medication that will require monitoring. The table below, summarizes the Vitamin C drug interaction groups.

Medication interaction	Interaction Category	Interaction Mechanism	Reference
Aluminum Hydroxide	Therapy modification Contraindicated for study purposes	Ascorbic Acid may increase the absorption of Aluminum Hydroxide, especially in patients with renal failure	Domingo JL, Gomez M, Llobet JM, Richart C. Effect of ascorbic acid on gastrointestinal aluminium absorption. Lancet . 1991;338(8780):1467. doi:10.1016/0140-6736(91)92776-x [PubMed 1683458]
Bortezomib	Therapy modification Contraindicated for study purposes	Ascorbic Acid may diminish the therapeutic effect of Bortezomib	Perrone G, Hidemitsu T, Ikeda H, et al, "Ascorbic Acid Inhibits Antitumor Activity of Bortezomib in Vivo," Leukemia , 2009, 23:1679-86.
Copper Depends on Dosage Form	Therapy modification Contraindicated for study purposes	Copper may decrease the serum concentration of Ascorbic Acid.	Prescribing information. Copper (cupric chloride). Lake Forest, IL: Hospira, Inc., 2004.
Deferoxamine Depends on Dose	Therapy modification Contraindicated for study purposes	Ascorbic Acid may enhance the adverse/toxic effect of Deferoxamine. Left ventricular dysfunction is of particular concern.	Prescribing information. Desferal (deferoxamine mesylate). East Hanover, NJ: Novartis Pharmaceuticals Corporation, September 2010.

Amphetamines, fluphenazine	Therapy modification Contraindicated for study purposes	Ascorbic Acid may decrease the serum concentration of Amphetamines. Documented discussion with patient, pharmacy and prescribing physician required.	Prescribing information. Adderall (dextroamphetamine and amphetamine). Wayne, PA: Shire US Inc., 3/07. Prescribing information. Dexedrine (dextroamphetamine). Research Triangle Park, NC: GlaxoSmithKline, July 2008.
CycloSPORINE (Systemic)	Monitoring required	Ascorbic Acid may decrease the serum concentration of CycloSPORINE (Systemic). Daily levels are required. Documented discussion with patient, pharmacy and prescribing physician required.	Lake KD, Aaronson KD, Gorman LE, et al, "Effect of Oral Vitamin E and C Therapy on Calcineurin Inhibitor Levels in Heart Transplant Recipients," J Heart Lung Transplant , 2005, 24(8):990-4. [PubMed 16102431] Prescribing information. Vyvanse (lisdexamfetamine). Wayne, PA: Shire US Inc., June 2013.
Estrogen Derivatives	Monitoring required	Ascorbic Acid may increase the serum concentration of Estrogen Derivatives. Documented discussion with patient, pharmacy and prescribing physician required.	Vihtamaki T, Parantainen J, Koivisto AM, et al, "Oral Ascorbic Acid Increases Plasma Oestradiol During Postmenopausal Hormone Replacement Therapy," Maturitas , 2002, 42:129-35. [PubMed 12065172]
Warfarin	Monitoring required	More frequent anticoagulation monitoring (daily INR checks) may be necessary upon initiation of warfarin therapy with concomitant ascorbic acid. Documented discussion with patient, pharmacy and prescribing physician required.	Sattar A, Willman JE, Kolluri R. Possible warfarin resistance due to interaction with ascorbic acid: case report and literature review. Am J Health Syst Pharm . 2013;70(9):782-786. [PubMed 23592361]
Aspirin	Depending on the dose	Aspirin may decrease the serum concentration of Ascorbic Acid if aspirin is used in the dosing range from 600 mg single dose up to 3.9 g/day. Documented discussion with patient, pharmacy and prescribing physician required.	Basu TK, "Vitamin C-Aspirin Interactions," Int J Vitam Nutr Res Suppl , 1982, 23:83-90. [PubMed 6811490]

Dobutamine, Depends on Route	Depending on the dose	Ascorbic Acid may enhance the positive inotropic effect of Dobutamine. Monitoring of mean arterial pressure is needed. Documented discussion with patient, pharmacy and prescribing physician required.	Mak S and Newton GE, "Vitamin C Augments the Inotropic Response to Dobutamine in Humans With Normal Left Ventricular Function," Circulation, 2001, 103(6):826-30. [PubMed 11171790]
Indinavir	Ascorbic Acid may decrease the serum concentration of Indinavir.	Documented discussion with patient, pharmacy and prescribing physician required.	Slain D, Amsden JR, Khakoo RA, Fisher MA, et al, "Effect of High-Dose Vitamin C on the Steady-State Pharmacokinetics of the Protease Inhibitor Indinavir in Healthy Volunteers," Pharmacother, 2005, 25(2):165-70. [PubMed 15767232]
Propranolol	Ascorbic Acid may decrease the serum concentration of Propranolol.	Ascorbic Acid may decrease the serum concentration of Propranolol. Documented discussion with patient, pharmacy and prescribing physician required.	Gonzalez JP, Valdivieso A, Calvo R, et al, "Influence of Vitamin C on the Absorption and First Pass Metabolism of Propranolol," Eur J Clin Pharmacol, 1995, 48(3-4):295-7. [PubMed 7589058]

Reference: Trissel's™ 2 Clinical Pharmaceutics Database

6.5.3 List of concurrent medications that should not be admixed, or Y-site administered during IV infusion

No other medication will be Y-site co-administered with intravenous vitamin C without first obtaining approval from hospital pharmacy services. Intravenous vitamin C will be administered through a dedicated IV-line, tubing and pump.

The table below includes medications with known and unknown incompatibility.

Intravenous Medication Y-site administered with IV Ascorbic Acid	Y-Site Incompatibility
Aminophylline	Incompatible
Azathioprine sodium	Incompatible
Ceftazidime	Incompatible
Ceftriaxone sodium	Incompatible
Chloramphenicol sodium succinate	Incompatible
Dantrolene sodium	Incompatible
Diazepam	Incompatible
Diazoxide	Incompatible
Erythromycin lactobionate	Incompatible
Etomidate	Incompatible
Ganciclovir sodium	Incompatible

Hydralazine hydrochloride	Incompatible
Hydroxocobalamin	Incompatible
Inamrinone lactate	Incompatible
Midazolam hydrochloride	Incompatible
Minocycline hydrochloride	Incompatible
Nitroprusside sodium	Incompatible
Papaverine hydrochloride	Incompatible
Pentamidine isethionate	Incompatible
Pentobarbital sodium	Incompatible
Phenytoin sodium	Incompatible
Sulfamethoxazole-trimethoprim	Incompatible
Thiopental sodium	Incompatible
Amphotericin B (conventional)	Unknown
Ampicillin sodium	Unknown
Ampicillin sodium-sulbactam sodium	Unknown
Propofol	Unknown
Haloperidol lactate	Unknown

Reference: Trissel's™ 2 Clinical Pharmaceutics Database

6.5.4 Drug or antibiotics interactions that may affected by urine acidification

Intravenous vitamin C may acidify the urine. Fluoroquinolones and macrolides function optimally in alkaline pH and may be affected by acidification of the urine. Fluoroquinolones, aminoglycosides, macrolides function optimally at alkaline pH. Tetracyclines, nitrofurantoin, many β -lactams exhibit highest activity under acidic conditions. Sulfamethoxazole, oxacillin, amoxicillin and clavulanic acid, vancomycin, imipenem, and clindamycin are unaffected by pH. Yang et al. (32).

6.6 Plasma Vitamin C quantification method

Plasma specimens are reduced with dithiothreitol (2mg/ml) followed by precipitation with 20% trichloroacetic acid then vortex-mixed and centrifuged. Supernate vitamin C levels are measured using high-pressure liquid chromatography (HPLC) with UV detection (via cGLP bioanalytical validation according to FDA guidelines on bioanalytical method validation). Chromatography is performed on a Zorbax SB-AQ, 4.6 x 150 mm, 5 μ m column (Agilent Technologies, Santa Clara, CA), with a mobile phase using a gradient buffer (dipotassium phosphate), ion pairing reagent (tretrabutyl ammonium chloride), and acetonitrile at a flow rate 0.850 mL/min. Detection will occur at 265 nm and vitamin C levels quantified using peak area analysis and external standardization. Ascorbic acid standards (5 - 2,500 μ M) are freshly prepared and treated in the same way as the test plasma samples. The limits of quantification are 5 μ M.

7 - Study Intervention Discontinuation and Participant Discontinuation/Withdrawal

7.1 Discontinuation of Study Intervention

There is no defined plan to discontinue the patients from the study, however, the PI may **stop** the vitamin C infusions prematurely in the following conditions, while the other interventions will continue for safety and study reasons:

The study drug will be **stopped** without the PI completely discontinue the study assessments for the patient (i.e. the patient will still participated in blood draw assessments, blood and urine tests per protocol and documentation of outcomes):

- If the patient status improves and patient **downgrades** level of care from ICU to lower levels of care (general or stepdown).
- if participants describe symptoms of **nephrolithiasis** (kidney stones) that is flank pain and hematuria with evidence of kidney stones in the imaging studies.
- do not tolerate the drug due to side effects such as nausea, vomiting, flushing, rash, headache, or diarrhea, the PI will discontinue the study if symptoms are **CTCAE v5 grade 3** or higher and not dose reduce the study drug. In this case the FDA will also be informed.
- if a patient develops a metabolic acidosis **unexplained** by other etiologies (e.g., lactic acidosis secondary to septic shock). Determination of the presence of metabolic acidosis will be made by the clinical care team.
- Study drug will also be **stopped** if the primary care team or surrogate decision-maker requests stopping the **drug for any reasons**. Data collection will continue for these patients following the withdrawal of study drug.

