5.1 Inclusion Criteria

- Adults of 18 years or older
- Patients hospitalized with a diagnosis of COVID-19 based on central laboratory-confirmed COVID-19 Novel Coronavirus Disease-2019, based on a positive SARS-CoV-2 RT-PCR confirmed **within 72 hours** prior to enrollment of nasal, oropharyngeal, or BAL specimen with hypoxemia, (i.e., decrease in oxygenation, as outlined below)
- Pulse oximetry saturation (SpO₂) < 93% on room air in WHO COVID-19 ordinal scale 3 patients, regardless the need for assisted ventilation, or oxygenation.
- Any new requirement of supplemental oxygen, with any oxygen device (WHO COVID-19 ordinal scale 4-7, regardless of pulse oximetry reading)
- In patients with supplemental oxygen at home, **any increase** in the requirement of supplemental oxygen.
- In ICU level of care

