5.5 Strategies for Recruitment and Retention

Non-intubated patients with COVID19 will be recruited from the Emergency Department (ED), the medicine inpatient wards, and the intensive care units (ICU) at VCU Medical Center and the Central Virginia VA Health System in Richmond, Virginia (RICVA). Both institutions are tertiary care medical centers with a large referral base. Study personnel will review patients within the electronic medical record to identify potential candidates for enrollment. Permission to approach patients and/or their families will be requested from the attending physicians in charge of patient care in the ED, inpatient unit, or the ICU. All patients meeting the inclusion/exclusion criteria will be approached with consent and will be entered into a screening log. If the patient is not enrolled, the screening log will include information explaining why enrollment did not occur (exclusion criteria, attending physician denial, patient refusal, etc.).

6 - Study Intervention

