- a. Concomitant medication use (if applicable): oxygen therapy (to calculate S/F ratio), oxygen device, antibiotics, COVID-19-specific (remdesivir, dexamethasone, tocilizumab, sarilumab, canakinumab, hydroxychloroquine, azithromycin, convalescent plasma, remdesivir) corticosteroids, albumin, thiamine, norepinephrine, vasopressin, and N-acetylcysteine, antiplatelet and anticoagulants, muscle relaxants, sedatives (propofol, midazolam) and opioid analgesia.
- b. Plasma levels: serum oxalate, creatinine, hematology, coagulation, biomarkers (ferritin, C - reactive protein (CRP), lymphocyte count, LDH, d-dimer). If the primary team does not obtain these tests, we will obtain them for study purposes (dedicated blood draw if needed on day 0 and 7) and as add-on-labs (no study-specific blood draw on days 1-4).
- c. Vital signs: Temperature, Respiratory Rate, Systolic and Diastolic Blood Pressures, Heart Rate, RASS score, Alert/ Not Alert, Oriented/ Not Oriented, FiO₂, oxygen delivery device.
- d. Ins/Outs: 24-hour oral or IV intake/output and dialysis/ CRRT details at midnight.
- e. Current ventilation status: use of mechanical ventilator or oxygen device (yes/no), mode, invasive/ non-invasive ventilation, FiO₂, PEEP, Plateau Pressure
- f. Ventilator/CCRT/Vasopressor/Delirium: last 7 days
- g. Adverse Events and tolerance: Interview with patient, may be conducted by telephone if feasible to reduce exposure of study personnel
- h. Mortality: date-time of death and all-cause mortality and likely cause of death.
- i. Discharge: Discharge date-time and discharge disposition (home, rehabilitation, skilled nursing facility, hospice, transfer to other hospital)
- j. For respiratory failure: was the patient at any time: turned to the prone position to facilitate oxygenation, paralyzed, placed on ECMO, had a tracheostomy placed?

Phase 1 End

- Total ventilator free days, CRRT free days, Vasopressor free days, and Delirium free days.
- Is patient still hospitalized?
- For respiratory failure, was the patient at any time: turned to the prone position to facilitate oxygenation, paralyzed, placed on ECMO, had a tracheostomy placed?
- Is patient still alive? If not, date/time and cause of death and code status at time of death.

Phase 2 follow-up (>=90 days)

- Is patient still alive? If not, date/time and cause of death and code status at time of death.

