The participant will provide informed consent prior to any procedures being done specifically for the study. Participants will be informed that participation is voluntary and that they may withdraw from the study at any time, without prejudice. Participants will be informed of other COVID-19 trials that are being performed. Should another drug become available to treat COVID-19 that is safe and effective the drug to subjects enrolled in this trial will be offered. A copy of the informed consent document will be given to the participants for their records. The informed consent process will be conducted and documented in the source document (including the date) and consent provided before the participant undergoes any study-specific procedures. The rights and welfare of the participants will be protected by emphasizing to them that the quality of their medical care will not be adversely affected if they decline to participate in this study.

Some of the patients approached for participation in this research protocol will have limitations of decision-making abilities due to their critical illness. Hence, some patients will not be able to provide informed consent. Accordingly, informed consent will be sought from the potential subject's legally authorized representative (LAR) in compliance with Federal Regulations 45 CFR part 46. Only those individuals who are authorized to serve as LARs per [VCU IRB Written Policies and Procedures #XI-3](#) will be eligible to provide consent on behavior of patients to participate in this study. Because all participants are inpatients in the hospital, the study will use the same LARs for research consent as are acting as LARs for the purposes of treatment.

10.1.1.b Informed Consent with DocuSign Part 11

In concordance with the latest FDA guidance on consent purposes, the study is offering electronic Informed Consent. This will be offered through DocuSign Part 11. The consent forms will be identical in Spanish and English; however, the signatures will be electronic. The electronic informed consent (eIC) will **only be offered** to Legally Authorized Representatives (LAR) **and not in face-to-face consent with patients. For face-to-face encounters only the paper consent forms will be used.**

The consents will be offered in order to facilitate the following:

- Legally Authorized Representative (LAR) may not be able to travel on site in a timely manner.
- LAR may not be comfortable visiting the hospital

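### The kidney-stone stop in section 7.1 depends on flank pain that the participant describes, so it is not met as worded in a sedated patient; separately, section 5.5 disagrees with 5.1, 5.2 and 6.3 on who is recruited.

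*Combined protocol and SAP*

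**What the plan says.** **The stop.** Section 7.1 lists conditions under which infusions end while assessments and data collection go on. The stone condition opens "if participants describe symptoms of" nephrolithiasis and defines this as "kidney stones) that is flank pain and hematuria with evidence of kidney stones in the imaging studies". The list is introduced as something the investigator may do; the next sentence says the drug will be stopped. The last bullet adds a general route: the drug is also stopped "if the primary care team or surrogate decision-maker requests stopping the" drug, with no particular reason required.

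**The patients.** Section 5.1 admits "Any new requirement of supplemental oxygen, with any oxygen device (WHO COVID-19 ordinal scale 4-7, regardless of pulse oximetry reading", at ICU level of care. Scores 6 and 7 are the ventilated states (section 3.1). Section 6.3 makes "WHO COVID-19 scale 6-7 at enrollment" its stratum B. Section 10.1.1 expects that "some patients will not be able to provide informed consent", and footnote a to the section 8.1.1 schedule records, where applicable, "muscle relaxants, sedatives (propofol, midazolam) and opioid analgesia".

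**What is recorded.** The Schedule of Activities has a kidney-stone row, completed in every column from Day 0-1 to Day 22-28. It lists a visibly passed stone and imaging consistent with a new stone as items distinct from back or flank pain and hematuria. Section 5.2 excludes anyone who has ever had an oxalate stone.

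**Recruitment.** Section 5.5 says: "Non-intubated patients with COVID19 will be recruited from the Emergency Department", and also names the medicine wards and the ICU.

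**The concern.** Kidney stones are a listed risk of the infusion (section 2.3.1), and part of the trial's rationale is to explore renal harm (section 4.2). A past oxalate stone bars entry, yet a stone seen or passed during treatment does not by itself end treatment. The rule needs a reported symptom, and the patients least able to report one are those under sedation. In them, stopping for a named drug risk rests on someone asking for it, so infusions could continue after a stone has been found and entered on the case report form.

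The section 5.5 wording is a different matter. It describes a population that the eligibility criteria and the randomization strata do not share.

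**Working it through.** There is no plan figure to reproduce. The check is a reading of the rule against the patients it covers, followed by simple dose arithmetic.

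**1. The rule as a logical test.** As worded, stop = (participant describes flank pain) AND (hematuria) AND (stone on imaging).

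| Patient | Flank pain described | Hematuria | Stone imaged | Stone stop met |
|---|---|---|---|---|
| Communicating, all signs | yes | yes | yes | yes |
| Sedated, hematuria and imaged stone | not obtainable | yes | yes | no |
| Sedated, visibly passes a stone, no imaging | not obtainable | yes or no | no | no |

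Hematuria can be observed without the patient's help. Flank pain is the element that cannot be obtained. The acidosis bullet in the same list leaves the determination to the clinical care team, so the section already contains a stop that needs no patient report.

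**2. Who can be in the lower rows.** Patients enrolled at WHO 6-7 (sections 5.1 and 6.3), and patients enrolled at lower scores and intubated during the 96 hours.

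**3. The other routes.**
- Care-team or surrogate request (7.1): works without patient report, but depends on a request.
- Adverse event stop (7.1 and 8.2.1): needs CTCAE grade 3 or higher. Under section 8.3.3 a finding that is observed only, with no intervention indicated, is grade 1. A stone with hematuria may be graded higher, but below grade 3 it does not trigger this stop.
- Dose halving (4.3 and 5.3.2): needs AKI stage 2 or 3, and reduces the drug without stopping it.

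**4. Remaining dose, illustrative.** Inputs: 16 infusions of 50 mg/kg every 6 hours (section 4.1), each capped at 3.75 g (section 4.3). Infusions given by hour h = h/6; section 8.1.1 agrees, placing the hour-48 sample before Infusion 9. Remaining = 16 − h/6. No doses are assumed skipped.

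| Stone found at hour | Remaining infusions | × 50 mg/kg | × 3.75 g (maximum) | If halved for AKI |
|---|---|---|---|---|
| 24 | 16 − 4 = 12 | 600 mg/kg | 45 g | 22.5 g |
| 48 | 16 − 8 = 8 | 400 mg/kg | 30 g | 15 g |
| 72 | 16 − 12 = 4 | 200 mg/kg | 15 g | 7.5 g |

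The full course is 16 × 50 = 800 mg/kg, at most 16 × 3.75 = 60 g. The hours are chosen for illustration, and the amounts apply to the vitamin C arm only.

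**5. Section 5.5 against the operative text.**
- Intubation: 5.5 says non-intubated; 5.1 admits WHO 4-7, 5.2 does not exclude intubated patients, and 6.3 stratifies on WHO 6-7 at enrollment.
- Setting: 5.5 names the emergency department and medicine wards; 5.1 requires ICU level of care and 5.2 excludes patients outside it.

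**The case against.** The strongest reply is that the last bullet of 7.1 already covers this case. It needs no patient report and it names the surrogate, who speaks for a sedated patient. No kidney imaging is scheduled, so an imaged stone would be incidental or clinically prompted, and either way it would probably reach the team able to require the stop. This stands. A reader might infer that the drug cannot be stopped in a sedated patient; the documents do not support that. What is absent is a stone-specific trigger that does not wait for a request.

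A second reply is that the bullet is loosely drafted under a lead-in that mixes may and will, so a strict three-part test is only one reading. That is fair, and it is also a reason to make the wording plain. Nor does intubated always mean unable to report: footnote c to the section 8.1.1 schedule records RASS and alertness because these vary.

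A reader might also infer that stones in such patients would go unrecorded because footnote g describes a patient interview for adverse events. That does not follow. The stone items are in the Schedule of Activities, section 8.2.1 requires monitoring every 24 hours in hospital, and section 8.3.4 gives further routes from consent onward.

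Finally, a reader might infer that 5.5 empties stratum B and so decides how many patients the gap reaches. It does not. Section 5.5 itself says that everyone meeting the inclusion and exclusion criteria will be approached, and patients can be intubated after enrollment.

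**Conclusion.** The point holds and is minor. As worded, the stone-specific stop is not met in a sedated or otherwise non-communicating patient who has hematuria with an imaged stone or who visibly passes one. Stopping then relies on a care-team or surrogate request.

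The documents do not give the number of patients affected, and it should be few. At most 30 patients receive vitamin C. Section 2.2 reports no stone formation at this dose in the earlier ARDS trial, which had 84 patients on vitamin C, although it notes that trial did not look specifically for oxalate nephropathy. No primary or secondary endpoint is affected. The remaining-dose figures show what could still be infused; they measure neither probability nor harm.

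The conclusion assumes that the stone bullet is read as written and that some participants are too sedated to indicate pain, which the consent and concomitant-medication text anticipates. The section 5.5 conflict is a real but separate consistency error.

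**What to change.** 1. **Section 7.1.** Replace the stone bullet with wording such as: *study drug is stopped if a stone is visibly passed, or if imaging shows a kidney stone not known before enrollment, whether or not the participant can describe symptoms.* The phrase about what was known before enrollment is deliberate: no baseline kidney imaging is scheduled, so a stone often cannot be shown to be new.

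2. **Section 5.5.** Delete the restriction to non-intubated patients, and update the emergency department and ward wording to ICU level of care, in line with 5.1, 5.2 and 6.3.

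**Cost.** Both are wording changes in a protocol amendment; the stone items are already collected. The downside of the first is an occasional stop for an incidental or pre-existing stone, in either arm because the study is blinded. Section 7.1 continues assessments after a stop, so outcome data are kept.
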